### Safety analysis during active treatment period (up to Week 52)

The safety analysis during active treatments will be based on the TSactive (excluding all data observed while patients were on placebo). All AEs, SAEs, AEs leading to discontinuation, drug related AEs, AESIs and lab PCSAs will be analysed from start of active treatment up to Week 52. The treatment grouping 6 will be presented for DINAMO and DINAMO Mono separately.

### Long term safety analysis (up to Week 52)

The long term safety analysis will be based on the TS (excluding patients initially randomised to placebo). All safety variables will be analysed from start of initial randomised treatment up to Week 52. The treatment grouping 5 will be presented for DINAMO and DINAMO Mono separately.

### Impact of assessment of up-titration to empagliflozin 25 mg (the period following the administration of the re-randomised medication planned at Week 14 up to Week 26/Week 52)

The up-titration safety analysis will be based on patients initially randomised to empagliflozin in the TS (only patients re-randomised at Week 14) for the assessment of up-titration to empagliflozin 25 mg. All AEs, SAEs, AEs leading to discontinuation, drug related AEs, AESIs, selected other specific AEs (hypoglycaemia, UTI, genital infections, acute pyelonephritis or urosepsis, bone fractures, AE related to reduced intravascular volume, and ketone measurements reported as AE) and lab PCSAs will be analysed. The treatment grouping 4 will be presented for DINAMO and DINAMO Mono separately.

### 7.8.1 Adverse events

AEs will be coded using the latest version of the MedDRA coding dictionary at database lock.

Any clinically significant new finding in the physical examination, vital signs and in the 12-lead ECG starting after Visit 2 (randomisation visit) will be considered as an AE and will be reported as such.

Unless otherwise specified the analyses of adverse events will be descriptive in nature and analyses of AEs will be based on the number of patients with AEs (not the number of AEs). All AEs will be reported according to the BI standard (5).

AE outputs for TG4 and TG5 will be presented for DINAMO only in Appendix 16.1.13 unless otherwise stated.

#### 7.8.1.1 Assignment of AEs to treatment

In general, the analysis of adverse events will be based on the concept of treatment emergent adverse events. This means that all adverse events occurring between first randomised or re-randomised drug intake until 7 days after last drug intake or cut-off (depending on analysis period, see [Section 7.8](#)) will be assigned to the randomised treatment.

In general, in-text AE tables will only present AEs assigned to the randomised treatment taken. For listings, AE will be assigned to one of the treatment phases of pre-treatment, treatment groups (depending on treatment grouping), post-treatment, post-study.

The cut off for the AEs outputs presentation period will be defined as the following.

- Prior to Week 26 treatment: Cut off at Visit 5 treatment date. If Visit 5 treatment date is not available, then the minimum of Day 183 or end of study date.
- Up to Week 52 present the whole treatment period plus the residual effect period.

#### 7.8.1.2 Analysis of other significant AEs

Other significant AEs will be reported and summarised according to ICH E3 criteria. Thus, AEs classified as 'other significant' will include those non-serious adverse events with:

- 'action taken = discontinuation' or 'action taken = reduced', or

- Marked haematological and other lab abnormalities or lead to significant concomitant therapy as identified by the Clinical Monitor/Investigator at a Medical Quality Review meeting or Blinded Report Planning Meeting.

Other significant AEs will be performed for the primary safety analysis and the safety during active treatment. See [Section 7.8](#) for details.

#### 7.8.1.3 AE summaries

An overall summary of adverse events will be presented by TG1, TG6, TG5 and TG4.

The frequency of patients with adverse events will be summarised by treatment, primary system organ class and preferred term. AEs will also be reported by intensity. Separate tables will be provided for patients with other significant adverse events according to ICH E3 (6), for patients with serious adverse events, for patients with AEs leading to discontinuation, for patients with drug-related AEs and for patients with selected AESIs and other specific AEs. Incidence rate as defined in [Section 7.8.1.8](#) will apply to frequency tables: overall summary of AEs, patients with AEs, patients with drug-related AEs, patients with other significant AEs according to ICH E3, patients with AEs leading to discontinuation and patients with SAEs. All above mentioned tables will be repeated by TG1, TG6, TG5 and TG4.

The system organ classes will be sorted in descending order of the total frequency count of all treatments then followed by preferred terms in descending order of the total frequency count. Alphabetical ordering will be used for the same total frequency counts on PT level.

Appendix 16.1.13 will include the following analyses by TG1 and TG6:

- Frequency of patients with AEs by SOC and preferred term
- Frequency of patients with SAEs by SOC and preferred term
- Frequency of patients with drug related serious AEs by SOC and preferred term
- Frequency of patients with adverse events by outcome, SOC and preferred term

Additionally, the following analyses will also be reported in Appendix 16.1.13 for disclosure on [clinicaltrials.gov](#) and [EudraCT](#):

- Frequency of patients with non-serious adverse events occurring with an incidence in preferred term greater than 5% by treatment, SOC and PT for disclosure on [clinicaltrials.gov](#).
- Frequency of patients with serious adverse events by treatment, SOC and PT for disclosure on [clinicaltrials.gov](#)
- AEs per treatment arm for disclosure on [EudraCT](#) (Number of patients exposed, affected by SAEs, affected by non-serious AEs with incidence > 5% in any treatment arm for each PT, number of death of all causes, number of deaths resulting from AEs will be presented.)

- Non-serious AEs with incidence > 5% in any treatment arm for each preferred term (grouped by standard SOC terms) for disclosure on EudraCT (Number of patients affected, exposed, total occurrences will be presented.)
- Serious AEs on preferred term (grouped by standard SOC terms) for disclosure on EudraCT (Number of patients affected, exposed, number of occurrences, occurrences causality related, fatalities, fatalities causally related to treatment will be presented.)

These result disclosure AE analyses in Appendix 16.1.13 will be performed using treatment grouping 9 for both DINAMO and DINAMO Mono together. See [\(13\)](#) for details.

#### 7.8.1.4 Protocol-specified AEs of special interest (AESI)

The protocol defines the following adverse events that for analysis purposes will be considered as AESIs:

- Hypersensitivity reactions (narrow SMQ) such as angioedema, angioedema-like events, and anaphylaxis
- Skin lesions (narrow SMQ) such as exfoliative rash, skin necrosis, bullous dermatitis
- Pancreatitis (narrow SMQ, PT)
- Pancreatic cancer (narrow BICMQ)
- Hepatic injury (narrow sub SMQ)
- Decreased renal function (narrow SMQ)
- Diabetic Ketoacidosis (DKA) (narrow BICMQ, investigator assessment)
- Events involving lower limb amputation (investigator-determined)

For those selected by SMQs/BICMQ, the list of AESIs and other specific AEs, which is maintained as a separate file (8-01-tsap-adverse-event-topics) in Section 8 TSAP and Programming in the TDMAP folder “Data Management and Statistics”. The current version at the time of DBL will be used to be in line with the current MedDRA version.

The frequency of patients with AESIs will be summarised by treatment, primary system organ class and preferred term.

These AESI analyses will be performed for the primary safety analysis (TG1), safety during active treatment (TG6), long term safety (TG5) and assessment of up-titration (TG4). See [Section 7.8](#) for details.

Events leading to lower limb amputation and DKA events will be listed only using the TS.

#### 7.8.1.5 Other specific adverse events

The analyses for the other specific adverse events will be performed for the primary safety analysis, safety during active treatment and selected other specific AE will be performed for the assessment of up-titration (Treatment grouping 1, 6 and 4 respectively).

## **Hypoglycaemia**

The investigator will record for each AE whether it represents a hypoglycaemic AE and, if so, record additional information to assess the intensity of the hypoglycaemic AE. On the basis of this information the investigator-defined hypoglycaemic AE will be classified as:

- Documented symptomatic hypoglycaemia AE with plasma glucose concentration  $\leq 70$  mg/dL ( $< 3.9$  mmol/L), as well as asymptomatic hypoglycaemia AE with plasma glucose concentration  $\leq 70$  mg/dL ( $< 3.9$  mmol/L)
- Documented (any) symptomatic and asymptomatic hypoglycaemia AE with plasma glucose concentration  $< 54$  mg/dL ( $< 3.0$  mmol/L)
- Severe hypoglycaemia AE: event requiring the assistance of another person to actively administer carbohydrates, glucagon or take other corrective actions. (Plasma glucose concentrations may not be available during an event, but neurological recovery following the return of plasma glucose to normal is considered sufficient evidence that the event was induced by a low plasma glucose concentration.)

Reported hypoglycaemia (investigator-defined hypoglycaemia) adverse event is defined as hypoglycaemia adverse event reported in the eCRF AE page.

Any hypoglycaemia (protocol-defined hypoglycaemia) is defined as reported hypoglycaemia adverse event or asymptomatic hypoglycaemia non-AE that had plasma glucose between  $\geq 54$  mg/dL ( $\geq 3.0$  mmol/L) and  $\leq 70$  mg/dL ( $< 3.9$  mmol/L).

Any hypoglycaemia that occurs on the same day, but, with a different start time, will be handled as a separate hypoglycaemic event.

The number and percentage of patients with reported hypoglycaemia AE will be tabulated by treatment, SOC and preferred term.

The characteristics of the episodes will be presented separately for the reported hypoglycaemia AEs and any hypoglycaemia.

Similarly as for the analysis on patient level, a summary on the number of any hypoglycaemia, descriptive event rate, number of episodes by severity will be produced per patient-years. Only apply to TG1 and TG6.

A frequency table will be provided for number and percentage of patients with symptomatic hypoglycaemia adverse event with confirmed plasma glucose  $< 54$  mg/dL ( $< 3.0$  mmol/L) and/or severe hypoglycaemia AE by baseline age at randomisation in categories. See [Table 6.4:1](#) for the subgroup details.

The treatment phase assignment of any hypoglycaemia (AE and non-AE) is exclusively based on the collected start date. These tables will be summarised up to the day before Week 26 by TG1 using TS, up to Week 52 by TG6 using TSactive and from the start of Week 14 to Week 52 by TG4 using TS (only patients re-randomised at Week 14) unless stated specifically.

### **Urinary tract and genital infections**

The following other specific adverse events will be assessed and be tabulated by treatment, SOC, PT:

- Genital infections (narrow sub BICMQ, investigator assessment)
- Urinary tract infections (UTI) (narrow sub BICMQ, investigator assessment)

In addition using the narrow sub BICMQ, serious genital infection events and genital infection events leading to treatment discontinuation will be summarised by treatment, SOC and PT. Similarly, the serious UTI events and the UTIs leading to treatment discontinuation will be summarised by treatment, SOC and PT.

Genital infections based on investigator assessment will be summarised by type (fungal balanitis or fungal vulvovaginitis, genital infection other than fungal balanitis or fungal vulvovaginitis), intensity (mild, moderate or severe), time to onset of first episode (within the first 3 months of treatment or after), duration (<7 days, 7-14 days and >14 days), how the event was treated (no treatment, therapy assigned, hospitalisation), treatment (0, 1, 2, >2 antimicrobials needed to treat), duration of treatment (≤7 days, >7 days), whether leading to discontinuation of treatment, and the number of events per patient.

Furthermore, the above mentioned displays on genital infections based on investigator assessment will be repeated by the type of infection (fungal balanitis or fungal vulvovaginitis, genital infection other than fungal balanitis or fungal vulvovaginitis).

UTIs based on investigator assessment will be summarised by intensity (mild, moderate or severe), time to onset of first episode (within the first 3 months of treatment or after), duration (<7 days, 7-14 days and >14 days), anatomical location (upper UTI (kidney), lower UTI (bladder and below)), how the event was treated (no treatment, therapy assigned, hospitalisation), treatment (0, 1, 2, >2 antimicrobials needed to treat), duration of treatment (≤7 days, >7 days), whether leading to discontinuation of treatment, and the number of episodes per patient.

These tables will be summarised up to the day before Week 26 by TG1 using TS, up to Week 52 by TG6 using TSactive and from the start of Week 14 to Week 52 by TG4 using TS (only patients re-randomised at Week 14).

### **Acute pyelonephritis or urosepsis**

Frequency of acute pyelonephritis (narrow sub BICMQ) or urosepsis (PT) will be tabulated by treatment, SOC and PT.

Acute pyelonephritis or urosepsis based on investigator assessment will be summarised overall and by intensity, and by additional treatment required (0, 1, 2, >2 antimicrobials needed to treat).

These tables will be summarised up to the day before Week 26 by TG1 using TS, up to Week 52 by TG6 using TSactive and from the start of Week 14 to Week 52 by TG4 using TS (only patients re-randomised at Week 14).

### **Bone fractures**

Bone fractures (narrow BICMQ) will be listed using TS.

### **Arthralgia**

Arthralgia (HLGT (primary path)) will be summarised by treatment, SOC and PT using TS (TG1) for up to the day before Week 26 and TSactive (TG6) for up to Week 52.

### **Pemphigoid in bullous conditions**

Pemphigoid in bullous conditions (HLT(primary path)) will be summarised by treatment, SOC and PT using TS (TG1) for up to the day before Week 26 and TSactive (TG6) for up to Week 52.

### **AE related to reduced intravascular volume (Volume depletion)**

Volume depletion (narrow BICMQ) will be listed and summarised by treatment, SOC and PT using TS (TG1) for up to the day before Week 26, TSactive (TG6) for up to Week 52 and TS with only patients re-randomised at Week 14 (TG4) from the start of Week 14 to Week 52.

### **Ketone measurements reported as AE**

Ketone measurements (narrow BICMQ) reported as AE will be summarised by treatment, SOC and PT using TS (TG1) for up to the day before Week 26, TSactive (TG6) for up to Week 52 and TS with only patients re-randomised at Week 14 (TG4) from the start of Week 14 to Week 52.

#### 7.8.1.6 Events qualifying for external adjudication by the Clinical Event Committee

Independent external Clinical Event Committee (CEC) regularly review cardiovascular, neurology, hepatic and ketoacidosis events and evaluate whether pre-specified criteria for these adjudication endpoints are met. Details on composition of the CECs, responsibilities and clinical event definitions are provided in separate CEC charters. Events qualifying for adjudication will be selected based on the latest CEC charter versions.

The CECs will be provided with additional, specified background material on the patients with these events and perform an assessment of the events. Result of adjudication assessments will be incorporated to the database.

Frequency table will be provided for adjudicated cardiovascular and neurological events, adjudicated hepatic events and adjudicated ketoacidosis events. All adjudication events and results will be listed.

This analysis will be performed for the primary safety analysis (TG1) and the safety during active treatment (TG6). For definition of safety analyses see [Section 7.8](#).

#### 7.8.1.7 AEs while patients taking wrong study medication

A listing using the TS will be provided for AEs that occurred while a patient was taking the wrong medication (planned and actual treatment taken) for DINAMO and DINAMO Mono separately.

#### 7.8.1.8 AE incidence rates

In addition to the frequency tabulations, time-adjusted adverse event analyses will be performed for on-treatment AEs and on-treatment AEs by SOC, respectively HLT and PT.

The time at risk in patient years for an AE is derived as follows:

Patients with AE:

time at risk (AE) in days = date of start of AE with specified PT/SOC/HLT – initial randomised treatment start date + 1

Patients without AE:

time at risk (AE) in days = end date of time at risk – initial randomised treatment start date + 1,

where end date of time at risk is the minimum of date of last study drug intake + x days and date of death, if applicable.

The standard approach will be x=7 days, but for certain AEs in addition other approaches will be used.

Total AE-specific time at risk per treatment group is then derived as:

Time at risk (AE) [years] = Sum of time at risk [days] over all patients in a treatment group/365.25

For 'each row of a table' (e.g. displaying an SOC), time at risk is calculated using start of first AE summarised in this row; e.g. for patient with AE in a specified SOC, time at risk = date of start of AE with specified PT in this SOC – start of initial randomised treatment + 1.

The AE incidence rate per 100 patient years at risk will then be calculated as follows:

Incidence rate per 100 patient years (pt-yrs) = 100\*number of patients with AE / time at risk (AE) [years].

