**Treatment grouping 3 (TG3) for Empagliflozin 10 mg titration period from Day 1 to Week 26:**

- *Placebo (Pbo)*
- *Empagliflozin titration start with 10 mg and dose remained at re-randomisation if needed (E Titr10)*, consisting of
  - Empagliflozin 10 mg responders at Week 12 to 10 mg (E10R-10)
  - Empagliflozin 10 mg non-responders at Week 12 to 10 mg (E10NR-10)
  - Empagliflozin 10 mg and not proceed to re-randomisation at Week 14 (E10)

**Treatment grouping 4 (TG4) for the period following the administration of the re-randomised medication planned at Week 14 up to Week 26/Week 52:**

- *Empagliflozin 10 mg after initial Empagliflozin 10 mg non-response (E10NR/10\*)*
- *Empagliflozin 25 mg after initial Empagliflozin 10 mg non-response (E10NR/25\*)*

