**Treatment grouping 9 (TG9) for AE result disclosure from Day 1 to Week 52:**

- *Placebo before re-randomisation at Week 26 (Pbo)*
- *Linagliptin 5 mg active pooled (L5 active)*, consisting of
  - Linagliptin 5 mg from the initial randomisation (L5)
  - Linagliptin 5 mg after initial placebo (P/L5\*)
- *Empagliflozin 10 mg active pooled (E10 active)*, consisting of
  - Empagliflozin 10 mg and not proceed to re-randomisation at Week 14 (E10)
  - Empagliflozin 10 mg responders at Week 12 to 10 mg (E10R-10)
  - Empagliflozin 10 mg non-responders at Week 12 to 10 mg (E10NR-10)
  - Empagliflozin 10 mg non-responders at Week 12 before re-randomisation to 25 mg (E10NR\*/25)
  - Empagliflozin 10 mg after initial placebo (P/E10\*)

- *Empagliflozin 25 mg active pooled (E25 active)*, consisting of
  - Empagliflozin 25 mg after initial Empagliflozin 10 mg non-response (E10NR/25\*)
  - Empagliflozin 25 mg after initial placebo (P/E25\*)

The treatment grouping TGx will be used according to the type of analysis, that has been assigned for each analysis throughout the TSAP. The treatment (or a combination of treatments) with the solid bullet point will be used in the analyses and the outputs presentation will use the short name as shown in bold in brackets. Each combination of treatments is defined by a list of treatments identifying the type and timing of the treatment. As a first example, the treatment identifier “E10R-10” means the patient was initially assigned to empagliflozin 10 mg and then carried on to empagliflozin 10 mg as a responder at Week 12, the entire treatment period is included. As a second example, the treatment identifier “E10NR/25\*” means the patient was initially assigned to empagliflozin 10 mg and then carried on to empagliflozin 25 mg as a non-responder at Week 12, but only the re-randomised treatment period from Week 14 is included.

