Table 6.3: 1 Patient sets analysed and treatment groupings (continued)

Class of endpoint	Patient sets					
	SCR	TS	TSactive	RS	mITT	PPS
Secondary efficacy endpoints						
Change in FPG [mg/dl] from baseline - ANCOVA					OC-AD-BOCF; OC (TG1)	
Change in body weight [kg] / SBP [mmHg] / DBP [mmHg] from baseline – MMRM					OC-AD; OC (TG1)	
Proportion of patients who achieve HbA1c goals < 6.5% and < 7.0%. Exact CI					NCF; OC (TG1)	

Table 6.3: 1 Patient sets analysed and treatment groupings (continued)

Class of endpoint	Patient sets					
	SCR	TS	TSactive	RS	mITT	PPS
Further safety endpoints						
Shift tables for the Tanner staging score from baseline		OC-AD (TG1, TG5)				
Descriptive statistics over time for growth velocity		OC-AD (TG1, TG5)				
Safety evaluation						
Overall summary of AEs		TG1, TG5, TG4	TG6			
Freq. of patients with the following AEs by treatment, SOC and PT 
 
• AEs
 
• AEs by worst intensity
 
• Drug-related AEs
 
• AEs leading to treatment discontinuation
 
• SAEs
 
• Other significant adverse events
 
• AESIs(except DKA and lower limb amputation)
 
		TG1, TG5, TG4	TG6			
Incidence rate of patients with AEs by treatment, SOC and PT		TG1, TG5				
List of patients with AESIs/other significant AE 
 
• DKA
 
• Events involving lower limb amputation
 
• Bone fracture
 
		TS				
Freq. of patients with other specific AE by treatment, SOC and PT: 
 
• Hypoglycaemic AE
 
• UTI (also investigator assessment, serious and leading to treatment discontinuation)
 
• Genital infection (also investigator assessment, serious and leading to treatment discontinuation)
 
• Acute pyelonephritis or urosepsis
 
• Volume depletion
 
• Ketone measurements
 
		TG1, TG4	TG6			

Table 6.3: 1 Patient sets analysed and treatment groupings (continued)

Class of endpoint	Patient sets					
	SCR	TS	TSactive	RS	mITT	PPS
Freq. of patients with other specific AE by treatment, SOC and PT: 
 
• Arthralgia
 
• Pemphigoid in bullous conditions)
 
		TG1	TG6			

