			7.8.1.1	
Removed the following text as no longer required. “Appendix 16.1.13 will display in addition AEs observed 'pre-treatment' (including AEs observed during screening and placebo run-in regardless of treatment group). Selected summaries will be created to include an analysis where AEs and SAEs are assigned to the following phases: pre-treatment, each treatment group (according to the type of analysis), and post-treatment.”

			7.8.1.3	
Updated paragraph to include more exposure adjusted AE tables according to FDA request: “Incidence rate as defined in Section 7.8.1.8 will apply to frequency tables: overall summary of AEs, patients with AEs, patients with drug-related AEs, patients with other significant AEs according to ICH E3, patients with AEs leading to discontinuation and patients with SAEs. All above mentioned tables will be repeated by TG1, TG6, TG5 and TG4.”.
 
Updated the sorting order for the AE table:            Old text “The system organ classes will be sorted in descending order of frequency then followed by preferred terms in descending order of frequency. Alphabetical ordering will be used for same frequency counts on PT level.” to            New text “The system organ classes will be sorted in descending order of the total frequency count of all treatments then followed by preferred terms in descending order of the total frequency count. Alphabetical ordering will be used for the total frequency counts on PT level.”.

Table 10: 4 History table for TSAP revised version dated 7th Jul 2022 (continue)

Version	Date	Author	Changes in old Section (new Section)	Brief description of change
Revised	7-JUL-2022		7.8.1.4	
Updated the following text:            Old text “Diabetic Ketoacidosis (DKA) (narrow BIcMQ)” to            New text “Diabetic Ketoacidosis (DKA) (narrow BIcMQ, investigator assessment)”.
 
Old text “Lower limb amputation and DKA events will be listed only using the TS.”. to            New text “Events leading to lower limb amputation and DKA events will be listed only using the TS.”.

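### The AE incidence-rate clock starts at the initial randomised dose, so TG4 and TG6 rates would be too low if they are produced as SAP 7.8.1.3 states

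*SAP*

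**What the plan says.** SAP 7.8.1.8 divides the number of patients with an AE by the total time at risk. Time at risk starts at the initial randomised treatment in all three places where it is defined: patients with the event, patients without it ("time at risk (AE) in days = end date of time at risk – initial randomised treatment start date + 1"), and the worked remark about table rows. It ends at the event or, for event-free patients, at last intake plus 7 days or death, whichever is earlier. No exception is made by treatment grouping.

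SAP 7.8.1.3 applies this definition to six AE tables and then says "All above mentioned tables will be repeated by TG1, TG6, TG5 and TG4". The history table entry of 7 July 2022 for that section reads "Updated paragraph to include more exposure adjusted AE tables according to FDA request". Table 6.3: 1 differs: its row "Incidence rate of patients with AEs by treatment, SOC and PT" lists only TG1 and TG5.

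The events that can be counted are set elsewhere:

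- **TG4** (SAP 6.1) is "for the period following the administration of the re-randomised medication planned at Week 14 up to Week 26/Week 52". The explanation of the treatment identifiers there says of such a group "but only the re-randomised treatment period from Week 14 is included".
- **TG6** (SAP 7.8) is analysed "excluding all data observed while patients were on placebo". Protocol 7.3.6 likewise limits placebo switchers to data after Week 26.
- **Assignment of AEs** (SAP 7.8.1.1) covers events "between first randomised or re-randomised drug intake until 7 days after last drug intake or cut-off", depending on the analysis period.
- **Exposure** (SAP Table 7.7: 1) starts for TG6 at the first active dose.

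**The concern.** A rate is interpretable only if its numerator and denominator cover the same period. Day 1 is the right start for TG1, for TG5 and for TG6 patients who were on active drug from the outset. It is wrong for TG4, whose events count only from Week 14, and for placebo patients who enter TG6 at Week 26. Both would bring time into the denominator during which, by the SAP's own rules, none of their events can enter the numerator. The rates can only be biased downwards.

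In TG6 the shortfall also differs by drug. Placebo patients are re-randomised 1:1:1 to linagliptin, empagliflozin 10 mg and empagliflozin 25 mg, so two thirds of them join the empagliflozin column and one third the linagliptin column. With equal true rates, empagliflozin would show the lower one. These are paediatric safety tables that were extended at a regulator's request.

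**Working it through.** The documents give no incidence rate or patient-years figure, so there is nothing to reproduce. The 7.8.1.8 formula was applied to the planned schedule.

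**Inputs**

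- First dose Day 1, Week 14 = Day 99, Week 26 = Day 183, Week 52 = Day 365 (SAP Table 6.7: 2).
- Residual period 7 days (SAP 7.8.1.8), so the end is Day 365 + 7 = 372.
- 50 patients per arm (Protocol 7.7.1) and 1:1:1 re-randomisation of placebo patients (Protocol 4.1.3): 50/3 = 16.7 to linagliptin and 33.3 to empagliflozin.
- Assumed: last intake on Day 365 and, in the base case, full completion.

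**Days at risk for an event-free patient**

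- From Day 1: 372 − 1 + 1 = 372
- From Day 99: 372 − 99 + 1 = 274, so 98 days are added by the Day 1 start
- From Day 183: 372 − 183 + 1 = 190, so 182 days are added

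**Rare events.** The rate shown divided by the true rate is the correct time over the time used.

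| Group | Correct time | Time used under 7.8.1.8 | Factor |
|---|---|---|---|
| TG4, per patient | 274 days | 372 days | 0.737 |
| TG6 empagliflozin | 50×372 + 33.3×190 = 24,933 days (68.3 patient-years) | 83.3×372 = 31,000 days (84.9) | 0.804 |
| TG6 linagliptin | 50×372 + 16.7×190 = 21,767 days (59.6) | 66.7×372 = 24,800 days (67.9) | 0.878 |

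The empagliflozin/linagliptin rate ratio is multiplied by 0.804/0.878 = 0.916.

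**Commoner events.** With constant hazard λ and T countable days, a patient has the event with probability p = 1 − exp(−λT) and contributes p/λ days on average. The Day 1 start adds a further d days (98 or 182), so for a group with a single start date the factor is (p/λ)/(p/λ + d). TG6 pools initially active patients (d = 0) with switchers (d = 182).

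| True rate per 100 patient-years | TG4 | TG6 empagliflozin | TG6 linagliptin | TG6 ratio |
|---|---|---|---|---|
| 5 | 0.733 | 0.801 | 0.875 | 0.915 |
| 10 | 0.729 | 0.797 | 0.873 | 0.914 |
| 20 | 0.722 | 0.790 | 0.867 | 0.911 |
| 100 | 0.663 | 0.732 | 0.823 | 0.890 |

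A true rate of 10 would thus be shown as about 7.3, 8.0 and 8.7. For one patient: a TG4 event on Day 109 counts as 109 days at risk, where 109 − 99 + 1 = 11 is correct.

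**Incomplete follow-up.** With 80% completing and leavers' last intake spread uniformly over Days 1 to 365, 90% of placebo patients reach Week 26. The rare-event factors are then 0.721 (TG4), 0.802 (TG6 empagliflozin) and 0.877 (TG6 linagliptin), with ratio 0.915.

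**The case against.** **Table 6.3: 1 may govern.** Its incidence-rate row is limited to TG1 and TG5, while neighbouring AE rows list TG4 and TG6 as well. The revision of 7 July 2022 also edited this table, and its visible entries record no change to that row. On that reading no biased rate is produced. This stands as a condition. However, the same revision deliberately extended 7.8.1.3 and quotes the sentence naming all four groupings, which makes an overlooked table row the likelier explanation. One of the two places needs changing in any case.

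**7.8.1.8 may be a generic formula, to be read with the period definitions.** Its end date is equally literal: for a TG1 completer it would run to about 372 days instead of about 182, although 7.8 and 7.8.1.1 already stop TG1 at Week 26. If those sections are allowed to set TG1's end, they might equally set the start for TG4 and TG6. The parallel is fair, and it shows that the end date needs attention too. It does not rescue the start date. The formula names the initial treatment three times, and the sections that set other periods contradict it without overriding it. The next section, 7.8.1.9, does adapt time at risk to re-randomised treatment and to the Week 26 cut-off; 7.8.1.8 does neither.

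**The sponsor's AE standard, cited in 7.8.1, may settle this.** It cannot be seen, so what will be programmed is not certain. The written rule is still wrong for these groupings.

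**The practical weight is modest.** This stands. At 10 per 100 patient-years, 68.3 and 59.6 patient-years give about 7 and 6 patients with events. The approximate 95% interval for their rate ratio is a factor of exp(1.96 × √(1/7 + 1/6)) ≈ 3 either way, so a distortion of 0.92 lies far inside the noise. The TG5 rates compare the two drugs over 52 weeks without switchers and are not affected by the start date.

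**Conclusion.** The concern holds, on condition that TG4 and TG6 rates are produced as 7.8.1.3 states. For rare events with full completion, the rates would be about 26% too low in TG4, and in TG6 20% too low for empagliflozin and 12% too low for linagliptin, with the TG6 ratio multiplied by about 0.92. These figures rest on equal arms of 50, equal three-way switching, planned visit days and last intake on Day 365. The direction does not depend on them. The shortfall grows for commoner events, and at 80% completion it hardly changes in TG6 and rises to 28% in TG4.

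The consequences are limited. The rates are descriptive, TG6 has no placebo column, and Protocol 7.3 says the trial is not powered to compare the two drugs. Patient counts, percentages and confirmatory tests are untouched. TG4 AE outputs are for DINAMO only and go to an appendix (SAP 7.8.1), and for rare events their 10 mg versus 25 mg ratio is preserved. It should be fixed because a stated rule gives a wrong number in safety tables and the correction is cheap.

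**What to change.** In all three places in 7.8.1.8, replace the initial randomised start by the first intake of the period analysed:

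- TG1 and TG5: first randomised intake.
- TG6: first active intake, as in Table 7.7: 1.
- TG4: first intake of the drug assigned at the Week 14 re-randomisation.

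Cross-refer the end date to the cut-off in 7.8.1.1, including its fallback when the Visit 5 treatment date is missing. Align that cut-off with the day-before-Week-26 rule in 7.8 and with the TG1 end date in Table 7.7: 1. Then make the incidence-rate row of Table 6.3: 1 and the list of groupings in 7.8.1.3 agree.

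The cost is SAP wording, one table row and one derivation. No new data are needed: the TG6 start and the Week 26 cut-off are already defined, and SAP 6.7 expects the Week 14 intake date and time to be recorded.
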